6.7 BASELINE, TIME WINDOWS AND CALCULATED VISITS

With regard to effectiveness and safety endpoints, the term "baseline" refers to the last observed measurement before administration of Ofev[®] Capsules. The first date of the administration of Ofev[®] Capsules is included in "baseline".

Effectiveness analyses will be performed based on calculated visits as shown in Table 6.7: 1. If two or more data points of a patient fall into the same interval, the closest value to the planned day will be selected. If there are two observations which have the same difference in days to the planned day or if there are two observations on the same day, the first value will be used.

Baseline, time windows and calculated visits Table 6.7: 1

		Time window (act	ual days on treatment)
Week label	Planned days	Start	End
Baseline	1		measurement before of Ofev® Capsules
Week 4	28	2	59
Week 13	91	60	136
Week 26	182	137	227
Week 39	273	228	318
Week 52	364	319	409
Week 65	455	410	500
Week 78	546	501	591
Week 91	637	592	682
Week 104	728	683	End of study

7. PLANNED ANALYSIS

For End-Of-Text (EoT) tables, the set of summary statistics is: N / Mean / SD / Min / Q1 / Median / Q3 / Max.

Tabulations of frequencies for categorical data will include all possible categories and will display the number of observations in a category as well as the percentage (%) relative to the respective treatment group (unless otherwise specified, all patients in the respective patient set whether they have non-missing values or not). Percentages will be rounded to two decimal places. The category missing will be displayed only if there are actually missing values.

7.1 DEMOGRAPHIC AND OTHER BASELINE CHARACTERISTICS

Only descriptive statistics are planned for this section of the report.

7.2 CONCOMITANT DISEASES AND MEDICATION

Concomitant diseases will be coded by the latest version of Medical Dictionary for Regulatory Activities (MedDRA). Only descriptive statistics are planned for concomitant diseases. Concomitant medication will be coded by latest version of "Nihon-iyakuhinshu".

7.3 TREATMENT COMPLIANCE

It is not planned to analyse treatment compliance.

7.4 PRIMARY ENDPOINT(S)

There is no primary endpoint for effectiveness as the primary objective of the PMS study is the evaluation of safety.

7.4.1 Primary analysis of the primary endpoint(s)

The analysis will be performed as defined in the NIS Protocol (see the NIS Protocol Section 7.3.1).

7.4.2 Sensitivity analysis, subgroup analysis, exploratory analysis of the primary endpoint(s)

The subgroup analysis for the frequency of patients with adverse drug reactions (ADRs) will be performed (see Section 6.4).

7.5 SECONDARY ENDPOINT(S)

7.5.1 Key secondary endpoint(s)

7.5.1.1 Primary analysis of the key secondary endpoint(s)

This section is not applicable as no key secondary endpoint has been specified in the NIS protocol.

7.5.1.2 Sensitivity analysis, subgroup analysis, exploratory analysis of the key secondary endpoint(s)

This section is not applicable as no key secondary endpoint has been specified in the NIS protocol.

7.5.2 (Other) Secondary endpoint(s)

For the absolute change from baseline in FVC [mL] at Week 104, descriptive statistics will be calculated. A 95% confidence interval for the mean change from baseline will also be calculated. In addition to the descriptive evaluation, the absolute change from baseline in FVC [mL] will be analysed using a mixed effects model for repeated measures (MMRM) approach.

MMRM analysis will includes all the available longitudinal observations at each post baseline visit during the treatment period. The statistical model includes baseline value as covariate, visit, gender, baseline age, baseline height, baseline FVC (or FVC% pred) and baseline FVC (or FVC% pred)-by -visit as fixed effect, and patients as random effect. The differences from baseline for each visit by patient are assumed to have a particular variance-covariance structure which is "unstructured". The SAS procedure MIXED will be used involving the restricted maximum likelihood estimation and the Kenward and Roger approximation of denominator degrees of freedom. Subsequently, LS means are computed at every time point and their respective standard error and 95% confidence interval estimate account for the estimated covariance parameters.

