4. CHANGES IN THE PLANNED ANALYSIS OF THE STUDY

Covariance matrix was changed from "compound symmetry" specified in NIS protocol to "unstructured" in MMRM (Mixed Effects Model for Repeated Measures) analysis.

Added the following events to priority survey items because they were added in Japanese RMP.

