6.3 SUBJECT SETS ANALYSED

The safety set will be the basis of all demographic, baseline and safety analyses. Effectiveness analysis will be done on the basis of the effectiveness set.

• Safety set:

This patient set includes all patients who didn't have any IPDs leading to exclusion from this analysis set as defined in Table 6.2: 1.

• Effectiveness set:

This patient set includes all patients with Ofev® Capsules in the safety set who were suffering from the approved indication. Further IPDs leading to exclusion from this analysis set are defined in Table 6.2: 1.

In FVC and %FVC analysis, patients with FVC and %FVC value at baseline and post treatment in effectiveness set are used.

Subject sets analysed Table 6.3: 1

	Subject set	
Class of endpoint	Safety set	Effectiveness set
Primary endpoints	X	
(other) Secondary and further endpoints		X
Safety endpoints	X	
Treatment exposure	X	X
Demographic/baseline endpoints	X	

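### Does the FVC mixed model add a redundant random patient effect to an unstructured covariance, and does that need a change?

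*SAP*

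**What the plan says.** Section 7.5.2 plans descriptive statistics and a 95% confidence interval for the mean change in FVC at Week 104, and adds a mixed model for repeated measures. The sentence that lists the terms begins "The statistical model includes baseline value as covariate, visit, gender, baseline age, baseline height, baseline FVC (or FVC% pred", adds the baseline-by-visit interaction, and closes with "as fixed effect, and patients as random effect". The next sentence reads "The differences from baseline for each visit by patient are assumed to have a particular variance-covariance structure" and names that structure as unstructured. The fit is by PROC MIXED with REML and Kenward-Roger degrees of freedom, after which "LS means are computed at every time point".

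Three other sections bear on this:

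- Section 4 records the departure from the protocol: "Covariance matrix was changed from 'compound symmetry' specified in NIS protocol to 'unstructured' in MMRM".
- Section 6.7 sets the time axis: "Effectiveness analyses will be performed based on calculated visits as shown in" Table 6.7: 1, which has nine post-baseline windows (Weeks 4, 13, 26, 39, 52, 65, 78, 91 and 104) and keeps one value per patient per window.
- Section 6.3 fixes the patients: "In FVC and %FVC analysis, patients with FVC and %FVC value at baseline and post treatment in effectiveness set are used".

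The SAP gives no program code for the model. It does not say in words that the patient is only the subject of the REPEATED statement.

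**The concern.** An unstructured matrix already leaves every variance and covariance between visits free. A random patient intercept adds the same constant to every cell of that matrix, so it can describe nothing new. A programmer who takes the sentence at its word would write both a RANDOM and a REPEATED statement and ask the software to separate two things the data cannot separate. That could bring a singular Hessian, a patient variance set to zero, or a fit that stops. Two programmers could also code the sentence differently, which a plan meant to give detailed procedures should prevent.

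Three smaller points lie close by:

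- The FVC baseline appears twice in the list of terms.
- No fallback is named if the unstructured fit fails.
- With gender as a classification factor and default margins, the LS means would weight men and women equally. This single-arm model has no treatment contrast in which that weighting would cancel.

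**Working it through.** The SAP states no parameter count, patient number or FVC variance for this model, so there is no figure of its own to reproduce. The check is a count, followed by a comparison of the two codings.

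**1. Covariance parameters.** Input: T = 9 post-baseline windows (Table 6.7: 1).

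- Unstructured matrix R: T(T + 1)/2 = 9 × 10/2 = 45 parameters.
- Adding a random patient variance τ²: 45 + 1 = 46 parameters.
- The marginal covariance is V = R + τ²J, with J a matrix of ones. V has 45 distinct elements, and the Jacobian of those elements with respect to the 46 parameters has rank 45. One parameter is not identified.
- Compound symmetry behaves the same way: with a random intercept added it has 3 parameters and rank 2. The change recorded in Section 4 therefore did not create the redundancy.

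**2. What the redundancy does to the results.** For any constant c, replacing τ² by τ² + c and R by R − cJ leaves V unchanged. The likelihood and the fixed-effect estimates depend on the covariance parameters only through V. The value τ² = 0 with R = V is always allowed, so both codings reach the same maximum.

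Kenward-Roger also agrees. V is linear in the parameters under either coding. Let I₀ be the information for the 45 parameters and D the 45 × 46 Jacobian. The information with 46 parameters is D′I₀D. Because D has full row rank, D(D′I₀D)⁻D′ = I₀⁻¹ for any generalised inverse. The small-sample adjustment is therefore the same.

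Simulated data bear this out. All settings are assumed, and they say nothing about FVC itself.

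| Check | Result |
|---|---|
| 200 patients, 9 visits, τ² = 0, 0.5, 1, 2 with R reduced to match | log-likelihood −3123.8496 each time |
| 80 patients, 9 visits, 30% missing, c = 0, 0.1, 0.3, 0.6 | −2 REML log-likelihood 940.685 each time |
| Same data, 45 or 46 parameters, generalised inverse | SE 0.2696 and df 59.23 in both |
| Same data, condition number of the information matrix | 44 without the random term, about 3 × 10¹⁶ (singular) with it |

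The last row is the numerical face of the rank result and the source of any warning.

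**3. The doubled baseline.** Columns: intercept 1, baseline 1, visit 9, gender 2, age 1, height 1, baseline FVC 1, baseline-by-visit 9, total 25. Without the duplicate there are 24. The rank is 9 (visits) + 1 (gender) + 1 (age) + 1 (height) + 9 (a baseline slope for each visit) = 21 in both cases. The fitted model is the same.

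**4. LS means and sex mix.** With equal weights, the offset from the observed mix is (p − 0.5) × d, where p is the male share and d the adjusted sex difference in change. The SAP gives neither. If p is 0.70 to 0.85 and d is 20 to 100 mL (both assumed), the offset runs from 0.20 × 20 = 4 mL to 0.35 × 100 = 35 mL. It is zero if d = 0 or p = 0.5.

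**5. Which reading the text supports.** The sentence after the list of terms attaches one covariance structure to the changes by visit within patient. Section 4 speaks of one covariance matrix, changed from one structure to another, and of no second variance component. Together these describe REPEATED visit with patient as subject and TYPE=UN. The remark about patients as random is most naturally taken as naming the patient as the unit within which observations are correlated.

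**The case for a change.** The best case for a change is that the SAP owns this specification. Section 3 says it gives detailed procedures for execution, and Section 4 shows that it replaced the protocol's covariance itself. A literal reader gets a model with one parameter too many, and clearer wording costs nothing. The counts of 45, 46 and 21 are right and do not depend on sample size. All of this stands as a remark on wording.

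It does not show that the plan would give a wrong answer. The two codings agree on every reported quantity if both fits complete. If the literal coding draws a warning, the analyst sees it at once, and the cure is to drop a term that adds nothing.

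The missing fallback is a gap of a kind that analysts fill if the need arises, and the protocol's analysis section, which is not at hand, may cover it. How likely a failed fit is cannot be judged, because the SAP gives no patient number or FVC completeness.

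The LS-mean point rests on a coding and on margins that the SAP does not state, and on an assumed sex share and sex difference. Equal or observed weights are a choice of target population. The unadjusted mean change at Week 104, with its 95% confidence interval, is reported beside the model in any case.

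**Conclusion.** No change to the plan is needed. Read literally, Section 7.5.2 has one redundant covariance parameter (46 where 45 can be identified) and one redundant baseline column (25 columns against 24, rank 21). Both are clerical. The marginal covariance, LS means, standard errors, degrees of freedom and intervals do not depend on which coding is used, provided that the fit completes. The remaining risk is a visible software warning with an obvious remedy, and its likelihood cannot be worked out from the SAP.

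The possible LS-mean offset of 4 to 35 mL depends wholly on assumed inputs, may be zero, and reflects a choice of weights. It does not show an error in the plan. The analysis is a supplementary model for a secondary effectiveness endpoint. It has no hypothesis test or treatment comparison, and the study's primary objective is safety.

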7.7 EXTENT OF EXPOSURE

Only descriptive statistics are planned for this section of the report.

7.8 SAFETY ANALYSIS

All safety analyses will be performed on the safety set.

7.8.1 Adverse events

Unless otherwise specified, the analyses of adverse events (AEs) will be descriptive in nature. All analyses of AEs will be based on the number of patients with AEs and NOT on the number of AEs.

Furthermore, for analysis of AE attributes such as duration, severity, etc. multiple AE occurrence data on the CRF, will be collapsed into AE episodes provided that all of the following applies:

[figure not shown]
- The same MedDRA lowest level term was reported for the occurrences
- The occurrences were time-overlapping or time-adjacent (time-adjacency of 2 occurrences is given if the second occurrence started on the same day or on the day after the end of the first occurrence)
- Treatment did not change between the onset of the occurrences OR treatment changed between the onset of the occurrences, but no deterioration was observed for the later occurrence

For further details on summarization of AE data, please refer to BI standards ('Analysis and Presentation of Adverse Event Data from Clinical Trials' (2))

AE analyses will be carried out after integrating AE data from CRF and AE data from Local PV safety database (Perceive).

In addition, events coded as "no adverse event", etc. will not be included in the AE analyses. The list of codes will be provided by Drug Safety.

The frequency of patients with the following items will be summarized by primary SOC and PT.

An ADR is defined as an AE for which either the investigator or the sponsor (or both) assess the causal relationship to Ofev® Capsules either as "Yes "or "Unknown". A serious AE is defined as an AE for which either the investigator or the sponsor (or both) assess the seriousness as "Serious".

The SOCs will be sorted according to the standard sort order specified by European Medicines Agency, PTs will be sorted by frequency (within SOC).

will also be reported by intensity. The frequency of patients having hepatic dysfunction at baseline with will be summarized. Patients with summarized by IIPs severity grade
To compare the risk of experiencing at least one ADR, in different patient subgroups, frequency tabulation stratified by different patient subgroups will be provided with odds ratios and exact 95% confidence intervals whenever specified (see Section 6.4). Logistic regression models will be used and odds ratios together with 95% confidence intervals will be provided.
Frequency tabulation of stratified by different patient subgroups (the following items) will be provided with odds ratios and exact 95% confidence intervals whenever specified. Logistic regression will be used for odds ratio.
Frequency tabulation of stratified by different patient subgroups (the following item) will be provided with odds ratios and exact 95% confidence intervals whenever specified. Logistic regression will be used for odds ratio.
Frequency tabulation of stratified by different patient subgroups (the following concomitant medications) will be provided with odds ratios and exact 95% confidence intervals whenever specified. Logistic regression will be used for odds ratio.

In addition, summaries for the time to onset of first episode for the ADRs will be tabulated, by duration (<=31, >31 to 91, >91 to 182, >182 to 273, >273 to 364, >364 to 455, >455 to 546, >546 to 637, >637 to 728, >728 [days]), by primary SOC, and PT.

The time to onset of the first adverse drug reaction categorized into priority survey items and diarrhoea will be tabulated by the time(0 to 14, 15 to 30, 31 to 60, 61 to 90, 91 to 180, 181 to 270, 271 to 360, 361 to 540, 541 to 727, =>728 [days]) and summarised.

Incidence rate of _____, ADRs and ______ will be summarized by person-year method, too. Pearson-year is defined as:

- if the patient has the event: date of onset of the first event date of first administration of Ofev® + 1 day
- if the patient did not have the event: date of last administration of Ofev® date of first administration of Ofev® + 1 day

Kaplan-Meier plots including the number at risk will be prepared for

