6. GENERAL ANALYSIS DEFINITIONS

6.1 TREATMENT(S)

For basic study information on treatments, please refer to NIS Protocol Section 5. The technical specification for treatment set-up is described in the analysis data set (ADS) plan. For safety analyses, data up to 28 days after last treatment intake will be considered as ontreatment.

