6.6 HANDLING OF MISSING DATA AND OUTLIERS

Safety:

Missing or incomplete AE dates are imputed according to BI standards (('Handling of Missing and Incomplete AE Dates' (1))).

Missing or partial date information other than AE and treatment dates will be replaced according to the following rules.

Effectiveness:

Missing effectiveness data will not be imputed.

Missing or partial date information will be replaced according to the following rules.

YEAR	MONTH	DAY	YMD	DT
"Unknown" (tick-box)		UNKNOWN		
уууу	Null or "Unknown"	Null	уууу	yyyy/01/01
уууу	mm	Null or "Unknown"	yyyymm	yyyy/mm/01

If the date of data which is collected after treatment of Ofev[®] Capsules in the CRF is before start of Ofev[®] Capsules, they will be set to missing.

Demographics:

Missing or partial date information in birth date will be replaced according to effectiveness

Treatment exposure:

Date of last Ofev® Capsules intake:

To calculate duration of Ofev® Capsules treatment at an interim analysis, the date is imputed with the following date according to the book number.

Book1: the first treatment date $+365.25/12 \times 3$

Book2: the first treatment date +365

Book3: the first treatment date $+365+(365.25/12\times6)$

Book4: the first treatment date +730 days.

Missing or partial date information will be replaced according to the following rules.

YEAR	MONTH	DAY	YMD	DT
уууу	mm	Null or "Unknown"	yyyymm	yyyy/mm/the last day of the month
уууу	mm	The beginning of the month	yyyymm	yyyy/mm/10
уууу	mm	The middle of the month	yyyymm	yyyy/mm/20
уууу	mm	The end of the month	yyyymm	yyyy/mm/ the last day of the month

Note that in general when tabulating AEs, and/or demographic and baseline characteristics variables reported as unknown will be treated as such; otherwise treated as missing data.

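### The visible subgroup comparisons of ADR risk in SAP Section 7.8.1 use odds ratios on a yes/no outcome and do not account for differing time at risk

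*SAP*

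**What the plan says.** Safety is the primary objective (SAP Sections 5.1 and 7.4). For subgroups, Section 7.4.2 states: "The subgroup analysis for the frequency of patients with adverse drug reactions (ADRs) will be performed". Section 7.8.1 gives the comparative aim and the method: "To compare the risk of experiencing at least one ADR, in different patient subgroups, frequency tabulation stratified by different patient subgroups will be provided", accompanied by odds ratios and exact intervals where specified, and then "Logistic regression models will be used and odds ratios together with 95% confidence intervals will be provided". Three further subgroup tables in that section, whose outcomes are blacked out, also use odds ratios from logistic regression. No offset, exposure covariate, fixed risk window or time-to-event model is visible for any of these comparisons.

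The counting unit is the patient: "All analyses of AEs will be based on the number of patients with AEs and NOT on the number of AEs". The window depends on each patient's last intake: "For safety analyses, data up to 28 days after last treatment intake will be considered as ontreatment" (Section 6.1). Follow-up runs to about two years. Table 6.7: 1 places Week 104 at day 728, and the interim rule for last intake in Section 6.6 ends with "Book4: the first treatment date +730 days".

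The plan does use time elsewhere in Section 7.8.1. ADR incidence "will be summarized by person-year method, too", first-ADR onset is tabulated in two sets of time bands, and Kaplan-Meier plots with numbers at risk are planned. Section 7.7 describes exposure. In the visible text none of these is tied to the subgroups.

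**The concern.** A patient treated for two months and one treated for two years each count once in the denominator. When an ADR-free patient stops, later ADRs cannot be seen, and that patient is scored as having had none. If one subgroup loses more ADR-free time this way than another, the odds ratio combines two things: how fast ADRs occur on drug, and how long patients were on drug to have one.

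The distortion can go either way. A subgroup with short ADR-free exposure may appear safer than it is, and a subgroup that stays on drug longer may be flagged as at risk for that reason alone. Because safety is the primary objective and these tables are where the plan sets out to compare risk between kinds of patient, a real risk factor could be missed or a false one reported.

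**Working it through.** The SAP states no ADR rate, stopping rate, death rate or subgroup size, so there is no figure of its own to reproduce. What follows is illustration under stated assumptions.

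**Model.** Let h be the hazard of a first ADR on drug (per year), m the hazard of stopping or death independent of ADRs, and T = 2 years.

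- Risk of at least one ADR: p = h/(h+m) × (1 − exp(−(h+m)T))
- Mean time at risk: (1 − exp(−(h+m)T))/(h+m)
- Odds ratio, B versus A: [pB/(1−pB)] / [pA/(1−pA)]

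**Equal ADR hazards.** Take h = 0.3 in both subgroups, with m = 0.2 in A and 0.7 in B. Ignoring ADRs, 1 − exp(−0.4) = 33% and 1 − exp(−1.4) = 75% have stopped by two years.

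- A: 0.3/0.5 × (1 − exp(−1.0)) = 37.9%
- B: 0.3/1.0 × (1 − exp(−2.0)) = 25.9%
- Odds ratio = (0.259/0.741)/(0.379/0.621) = 0.57

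The true hazard ratio is 1.00. Comparing A with B instead gives about 1.74, so the longer-treated subgroup looks at risk. Adding to p the ADRs that occur in the 28 days after stopping, m/(h+m) × (1 − exp(−(h+m)T)) × (1 − exp(−28h/365.25)), gives 38.5% and 27.3%, odds ratio 0.60.

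**True excess in B.** With h = 0.45 in B (hazard ratio 1.5), risk in B is 0.45/1.15 × (1 − exp(−2.3)) = 35.2% and the odds ratio is 0.89. The direction reverses.

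**Range with equal ADR hazards.**

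| ADR hazard per year | Stopping hazard, A vs B | Risk, A vs B | Odds ratio |
|---|---|---|---|
| 0.1 | 0.2 vs 0.4 | 15.0% vs 12.6% | 0.82 |
| 0.3 | 0.2 vs 0.7 | 37.9% vs 25.9% | 0.57 |
| 1.5 | 0.3 vs 1.0 | 81.1% vs 59.6% | 0.34 |
| 1.5, first 3 months only | 0.2 vs 0.7 | 30.5% vs 28.8% | 0.92 |
| 3, first 3 months only | 0.3 vs 1.0 | 51.1% vs 47.4% | 0.86 |

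The last two rows use the same formula with T = 0.25. With the 28-day tail, the constant-hazard extremes become 0.83 and 0.37.

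**Stopping only after a first ADR.** Every ADR-free patient is then followed for the full period. Risk is 1 − exp(−hT) in both subgroups and the odds ratio is 1.00.

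**Is a person-year ratio enough?** Under constant hazards it recovers the true ratio. Under early clustering it does not. Take an identical hazard of 1.6 per year in the first 3 months and none later, with fixed exposures of 0.75 and 1.5 years.

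- Risk in both: 1 − exp(−0.4) = 33.0%, so the odds ratio is 1.00
- Mean person-time, short exposure: 0.330/1.6 + 0.670 × 0.50 = 0.541 years
- Mean person-time, long exposure: 0.330/1.6 + 0.670 × 1.25 = 1.044 years
- Rate ratio: (0.330/0.541)/(0.330/1.044) = 1.93

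Here the person-year ratio reports a difference that does not exist. A Cox model compares patients at the same time since start and gives 1.00.

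**The case against.** The strongest reply has four parts.

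First, a reader might infer that the plan ignores time on drug. It does not: Section 7.8.1 has person-year rates, onset tables and Kaplan-Meier plots. The point is confined to the subgroup comparison. Even there it covers only visible text. Section 6.4, which the SAP cites for the subgroups, is not available, and several outcomes, including everything the Kaplan-Meier sentence applies to, are blacked out. A time-based subgroup analysis may exist in that text, and no omission from the full plan can be claimed.

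Second, a reader might infer that sicker patients stop or die sooner and so look safer. The document gives no figures on this. The direction of any bias is unknown.

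Third, the effect may be small. If ADRs come early it shrinks, and if ADRs cause the stopping it vanishes. The fine early onset bands (0 to 14 and 15 to 30 days) suggest close interest in early ADRs, though the bands run beyond day 728, so the plan does not assume that ADRs are only early.

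Fourth, AE analyses are descriptive unless otherwise specified, no visible decision rule rests on these odds ratios, and the share of treated patients with an ADR is a legitimate summary of risk in practice.

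All four limit the size or scope of the point. None removes it. The plan states an aim of comparing risk, and the odds ratio alone cannot show whether a difference comes from ADR rate or from time on drug. The fourth is a good reason to keep the odds ratios.

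**Conclusion.** The point holds in limited form. In the visible text, subgroups are compared on ADR occurrence only by odds ratios and logistic regression, while time at risk varies by patient. Where subgroups differ in ADR-free time on drug, the odds ratio reflects both exposure and ADR risk.

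The size is an assumption throughout. It depends on constant or early hazards, on stopping independent of ADRs, on a two-year horizon and on the chosen stopping rates. Within those scenarios the distortion ranges from none to an odds ratio of about 0.34 when the true ratio is 1. The documents do not allow a choice among the scenarios. This is a cheap improvement to a descriptive analysis and does not make the planned tables invalid.

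**What to change.** In Section 7.8.1, for the same subgroups:

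- Keep the frequency tables and odds ratios.
- Add a Cox model for time from first administration to first ADR, with ADR-free patients censored at the end of the on-treatment window. Report hazard ratios with 95% confidence intervals.
- Show median exposure and person-years per subgroup beside the odds ratios.
- Do not rely on a constant-rate Poisson ratio alone, since it misleads when ADRs cluster early.
- Align the two definitions of time at risk. Person-time without an event ends at last administration (Section 7.8.1), whereas on-treatment safety data run 28 days longer (Section 6.1). As written, an ADR in those 28 days can count as an event while event-free patients contribute no time there.

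The Cox model needs no constant ADR hazard, but it assumes a roughly stable hazard ratio over time, and that within a subgroup stopping is unrelated to an impending ADR. If Section 6.4 or the blacked-out text already provides such an analysis, a cross-reference is enough.

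The cost is SAP wording, one more model per subgroup table and a somewhat longer table set. Onset dates and first and last administration dates are already used for the person-year calculation, so no new data are needed.

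### The person-year ADR rate can count events up to 28 days after the last capsule but stops event-free time at the last capsule, so it is biased upward

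*SAP*

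**What the plan says.** Section 6.1 of the SAP sets the general rule: "For safety analyses, data up to 28 days after last treatment intake will be considered as ontreatment".

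Section 7.8.1 then gives the person-time for an incidence rate of ADRs and of other items that are blacked out. Both branches are read here as a difference of dates plus one day, counted from first administration. They have different end points:

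- Patient with the event: "if the patient has the event: date of onset of the first event". Nothing limits onset to the period up to last intake.
- Patient without the event: "if the patient did not have the event: date of last administration of Ofev". Nothing adds the 28 days.

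The ADR definition in the same section depends on causality alone and sets no limit on the onset date.

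**The concern.** A person-time rate is interpretable only if every patient is counted as at risk over exactly the period in which an event would be counted. Here an ADR 20 days after the last capsule enters the numerator under section 6.1 and brings its 20 post-treatment days with it. A patient observed over those same days without an ADR contributes none of them. Only event-free time is lost, so the error has one direction.

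Safety is the primary objective of this study, and this is the plan's exposure-adjusted ADR rate. The distortion grows as treatment gets shorter. It therefore matters most when the rate is compared with a source of different treatment duration.

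**Working it through.** The SAP states no figure for this point, so there is none to reproduce. The check is a two-patient illustration followed by a cohort calculation.

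**Two patients.** Both take the last capsule on day 100. One has a first ADR on day 120. The other is event-free and observed to day 128.

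| Rule | Events | Person-days | Rate per person-year |
|---|---|---|---|
| As planned | 1 | 120 + 100 = 220 | 365.25/220 = 1.66 |
| (a) Common window, last intake + 28 days | 1 | 120 + 128 = 248 | 365.25/248 = 1.47 |
| (b) Common window ending at last intake | 0 | 100 + 100 = 200 | 0 |

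The planned figure matches neither consistent definition. The example shows the mechanism; with its only event placed after stopping, it says nothing about size.

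**Cohort, inputs.**
- From the SAP: the 28-day period (section 6.1) and the two person-time rules (section 7.8.1).
- Assumed, because the SAP gives none of them:
  - exponential stopping, with 20%, 40% or 60% stopped by day 365 for reasons other than the event;
  - follow-up to day 730;
  - on-drug event rate of 0.05, 0.3 or 1.0 per year;
  - hazard in the 28 days after stopping equal to k times the on-drug hazard, with k = 1, 0.5, 0.1 or 0.
- Day 730 is a working assumption close to the last planned day of 728 in Table 6.7: 1. The rule "Book4: the first treatment date +730 days" in section 6.6 is an interim imputation and does not define a follow-up limit.

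**Hand check for rare events.** Let μ = -ln(1 - p) be the yearly stopping rate and r = 28/365 = 0.0767 years. Mean time on drug up to the cap is (1 - e^(-2μ))/μ, and mean post-treatment time is about (1 - e^(-2μ)) × r. Post-treatment time relative to on-drug time is therefore μr.
- Planned rate / rate (a) ≈ 1 + μr, because the planned denominator omits nearly all post-treatment time.
- Planned rate / rate (b) ≈ 1 + kμr, because the planned numerator includes post-treatment events.

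| Stopped by one year | μ | μr (k = 1) | 0.5μr | 0.1μr |
|---|---|---|---|---|
| 20% | 0.223 | 1.7% | 0.9% | 0.2% |
| 40% | 0.511 | 3.9% | 2.0% | 0.4% |
| 60% | 0.916 | 7.0% | 3.5% | 0.7% |

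**Simulation, 2,000,000 patients per scenario.**

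| Ratio | 20% | 40% | 60% |
|---|---|---|---|
| Planned / (a), all event rates | 1.016-1.017 | 1.036-1.039 | 1.065-1.070 |
| Planned / (b), rate 0.3, k = 1 | 1.017 | 1.038 | 1.069 |
| Planned / (b), rate 0.3, k = 0.5 | 1.008 | 1.019 | 1.034 |
| Planned / (b), rate 0.3, k = 0.1 | 1.002 | 1.004 | 1.007 |
| Planned / (b), rate 0.3, k = 0 | 1.000 | 1.000 | 1.000 |

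The hand check agrees. With no early stopping the ratio is 1.000. Letting 30% of event patients stop because of their event left the ratios at 1.016-1.017, 1.038 and 1.068 (rate 0.3), since only event-free stoppers lose time.

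**Upper bound.** Suppose every patient is treated for T years and then observed for the full 28 days at constant hazard h. Events per patient are E = 1 - exp(-h(T + r)), consistent person-time is E/h, and planned person-time is E/h - exp(-h(T + r)) × r. With h = 0.2 and T = 0.5, E = 0.1089, consistent time is 0.5447 years and planned time is 0.5447 - 0.8911 × 0.0767 = 0.4763 years. The planned rate is 0.1089/0.4763 = 0.229 instead of 0.20, a ratio of 1.14. For h from 0.05 to 1.0 the ratio is 1.11-1.15 at 6 months on drug and 1.25-1.30 at 3 months.

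**The case against.** The strongest objection is about size and use. The person-year rate supplements the frequency tables, and section 7.8.1 says "Unless otherwise specified, the analyses of adverse events (AEs) will be descriptive in nature". No visible test or threshold depends on the rate, and the visible subgroup comparisons use odds ratios. The upper bound requires all patients to stop early with a full 28 days observed, which is unrealistic for the whole cohort. If the hazard falls sharply after stopping, the planned rate is within 0.2-0.7% of a rate confined to time on drug. Death or loss to follow-up soon after the last capsule would shrink the bias further. All of this stands and limits the importance of the point.

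A second objection is that the company standard cited for AE summaries, or the analysis data set plan cited in section 6.1, may settle which events count. Neither is visible. Section 7.8.1 nevertheless writes out its own formula, and a programmer would follow it. If only events up to last intake are meant, the section must say so, because section 6.1 states the opposite for safety analyses in general.

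**Conclusion.** The concern holds. Sections 6.1 and 7.8.1 together give the ADR rate two different risk periods, and no visible text reconciles them. The other rated items are blacked out but share the same definition.

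Under the assumed stopping rates of 20-60% by one year, the planned rate is about 1.6% to 7.0% too high against a common 28-day window, almost regardless of the hazard after stopping. Against a window ending at last intake, the excess runs from 0 to about 7%, depending on that hazard. These figures assume that stoppers are observed for the 28 days. The inconsistency itself needs no assumption. It should be fixed, although it is unlikely to change the overall safety picture.

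**What to change.** State one risk window in section 7.8.1 that governs both events and time. Either version is sound:

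- **(a) In line with section 6.1:** end event-free time at the earliest of last administration plus 28 days, death and end of observation, and count first events only within that interval.
- **(b) As a stated exception to section 6.1:** count only first events with onset up to last administration, and cap all person-time there.

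It is sensible to censor the Kaplan-Meier plots in the same section at the same date. Their outcomes and any censoring rule are blacked out, so this is a point of consistency and not a separate finding.

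The cost is one line of SAP wording and one derived date, with no new data. Under the assumed stopping rates the reported rate would fall by at most about 7%.
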